## STUDY SYNOPSIS

STUDY TITLE	A Phase II basket study of the oral selective pan-FGFR inhibitor Debio 1347 in subjects with solid tumors harboring a fusion of FGFR1, FGFR2 or FGFR3.		
STUDY NUMBER	Debio 1347-201	STUDY PHASE	II
STUDY DESIGN	Multicentre, basket, two stage, adaptive single arm Phase II study in subjects with solid tumors harboring FGFR1-3 gene fusion/rearrangement. Three cohorts will be included consisting of subjects with biliary tract cancer (Cohort 1), urothelial cancer (Cohort 2) and all other solid tumor histologies not included in Cohorts 1-2 such as NSCLC, head and neck cancer, thyroid cancer, oral cancer, breast cancer, prostate cancer and others but excluding primary brain tumors (Cohort 3).		
STUDY OBJECTIVES	
Primary objective
 
To assess the efficacy of Debio 1347 in terms of ORR in subjects with solid tumors harboring FGFR1-3 gene fusion/rearrangement.
 
Secondary objectives
 
 
To evaluate the efficacy of Debio 1347 in terms of DoR, DCR, PFS and OS.
 
To assess the safety of Debio 1347.
 
To assess exposure-response relationships vs efficacy and safety (notably QTcF).
 
 
[REDACTED]
 
[REDACTED]
 
[REDACTED]
 
[REDACTED]
 
[REDACTED]
 
[REDACTED]
 
[REDACTED]
 
[REDACTED]
 
[REDACTED]
 
[REDACTED]
		
ENDPOINTS	
Primary endpoint
 
ORR (defined as the proportion of subjects with a BOR of partial or complete response) as centrally measured by RECIST 1.1 criteria.
 
Secondary endpoints
 
 
DoR (defined as the time from the date of the initial partial or complete response to date of the first documented progression or death due to any cause).
 
DCR (defined as the proportion of subjects with a BOR of CR or PR or SD).
 
PFS (defined as the time from the start date of treatment to date of the first documented progression or death due to any cause).
 
OS (defined as the time from the start date of treatment to date of death due to any cause).
 
Proportion of subjects with TEAEs assessed by NCI-CTCAE v5.0 and SAEs.
 
Debio 1347 plasma exposure (<math>C_{trough}</math>, <math>AUC_{\tau}</math> and any other PK parameters as deemed appropriate) and relationships with efficacy and safety endpoints; Debio 1347 plasma concentration (C)-QTcF relationship based on ECG and PK matching time-points.
 
 
[REDACTED]
 
[REDACTED]
 
[REDACTED]
 
[REDACTED]
 
[REDACTED]
 
[REDACTED]
 
[REDACTED]
 
[REDACTED]
 
[REDACTED]
 
[REDACTED]
 
[REDACTED]
 
[REDACTED]
 
[REDACTED]
		
STUDY POPULATION	Subjects with locally advanced (unresectable) or metastatic tumors with FGFR1-3 gene fusion/rearrangement who require systemic therapy and who have radiologic and/or clinical progression following at least one prior standard treatment or who have no satisfactory alternative		

	treatment options will be included in this study. Approximately 125 males or females $\geq 18$ years will be recruited in North America, EU, the Middle East, South America and the Asia Pacific region.
INCLUSION CRITERIA	
 
1. Written informed consent given according to ICH/GCP guidelines and local regulations.
 
2. Cytologically or histologically confirmed advanced solid tumor.
 
3. Radiographic progression on prior systemic therapy; prior localized therapy (i.e., radiation, ablation, embolization) is allowed provided radiographic progression out-of-field or in the treatment field is shown.
 
4. Male or female <math>\geq 18</math> years of age.
 
5. Locally-advanced (unresectable) or metastatic disease harboring an FGFR1-3 gene fusion/rearrangement potentially leading to a functional FGFR aberrant protein, identified through local and/or central molecular assay.
 
6. The subject must have received at least one prior line of standard therapy appropriate for tumor type and stage of disease (if available), and, in the opinion of the Investigator, s/he would have been unlikely to tolerate or derive clinically meaningful benefit from further appropriate standard of care therapy. In particular: 
 
a. Biliary tract cancer subjects must have progressed on/after gemcitabine-based chemotherapy (including subjects who progressed within 6 months of gemtabcine-based adjuvant chemotherapy). Subjects can have received additional chemotherapy after documented intolerance to gemcitabine.
 
b. Urothelial cancer subjects must have progressed on/after cisplatin-based or carboplatin-based chemotherapy either given for advanced disease or within 12 months from completion if given as neoadjuvant or adjuvant therapy and anti-PD1/PDL1 therapy (unless not available, contraindicated for some reasons or refused by the patient).
 
c. NSCLC subjects must have progressed on chemotherapy and anti PD1/PDL1 therapy (unless contraindicated for some reasons). Subjects with known EGFR mutations, ALK rearrangement or BRAF V600E mutation must have received the relevant target therapy (unless not available).
 
d. For all other tumor types, subjects must have progressed on/after appropriate SOC therapy (evidence-based level 1). Subjects who harbor genomic aberrations for which approved target therapy is available must have received such therapy. HER2+ or ER/PR+ breast cancer subjects should have received at least one line of HER2-targeted or ER-targeted, respectively.
 
 
 
7. Measurable disease according to RECIST criteria version 1.1.
 
8. ECOG PS of 0 to 1.
 
9. Screening laboratory values as follows: 
 
a. ANC <math>\geq 1,000/\text{mm}^3</math> [<math>1.0 \times 10^9/\text{L}</math>].
 
b. Platelet count <math>\geq 75,000/\text{mm}^3</math> [<math>75 \times 10^9/\text{L}</math>].
 
c. Hemoglobin <math>\geq 8.0</math> g/dL.
 
d. Total bilirubin <math>\leq 2 \times \text{UNL}</math> [biliary stent allowed]. A subject with an isolated elevation of indirect bilirubin is eligible.
 
e. AST and ALT <math>\leq 2.5 \times \text{UNL}</math> (<math>5 \times \text{UNL}</math> in the presence of liver metastases).
 
f. Calculated or measured creatinine clearance <math>\geq 30</math> mL/min (creatinine clearance measured based on 24-hour urine collection should be considered to help assess eligibility).
 
g. Serum phosphate <math>< 1.5 \times \text{UNL}</math>.
 
 
 
10. Female subjects of child-bearing potential must have a negative serum pregnancy test (minimum sensitivity of 25 mIU/mL) at screening and be willing to practice the highly effective contraception methods listed below from the time of study entry up to 6 months after the last day of treatment: 
 
a. IUD
 
b. IUS
 
c. Bilateral tubal occlusion
 
d. Vasectomized partner
 
e. Sexual abstinence if corresponds to usual and preferred lifestyle of subject.
 
 
For hormonal contraceptives see Section 7.7.1
 
Of note:
 
 
- Female subjects of non-childbearing potential are defined as either pre-menopausal with a documented tubal ligation or hysterectomy or post-menopausal with 12 months of spontaneous amenorrhea.
 
- Female subjects of child-bearing potential must refrain from donating egg(s) during the clinical study and for 6 months after Debio 1347 discontinuation.
 
- Male subjects must agree to use a condom from study entry and up to 6 months after the last day of treatment. The subject's female partner should use highly effective contraception
 
 
 


	
methods, which may include hormonal contraceptives or any of the methods outlined above, during this period.
 
 
- Male subjects must refrain from donating sperm during the clinical study and for 6 months after Debio 1347 discontinuation.
 
 
11. Available fresh tumor sample (preferably) or, if no fresh sample can be obtained, archived tumor sample (slides or block) for central analysis of FGFR status or retrospective central confirmation in case of local screening.
 
Of note: A "liquid biopsy", e.g., ctDNA based test is acceptable for subject eligibility but then a pre-study treatment tissue sample is required for post-hoc confirmation of the fusion.
 
12. Life expectancy <math>\geq</math> 3 months.

EXCLUSION CRITERIA	
 
1. History of hypersensitivity to any of the excipients in the Debio 1347 formulation (lactose hydrate, microcrystalline cellulose, croscarmellose sodium, hydroxypropyl cellulose, sodium lauryl sulfate and magnesium stearate).
 
2. Prior treatment with a FGFR1-3 selective inhibitor.
 
3. History and/or current evidence of ectopic mineralization/calcification, including but not limited to soft tissue, kidneys, intestine, myocardia, or lung, excepting calcified lymph nodes, lung nodules and asymptomatic vascular or cartilage/tendon calcifications.
 
4. Current evidence of clinically significant corneal or retinal disorder confirmed by ophthalmologic examination.
 
5. Chemotherapy, radiotherapy or small molecule anti-cancer agents within 2 weeks prior to initial dosing with Debio 1347 (3 weeks for immune checkpoint inhibitors).
 
6. Administration of any investigational agent within 2 weeks prior to initial dosing with Debio 1347 (3 weeks for immune checkpoint inhibitors).
 
7. Surgery requiring general anesthesia, except diagnostic biopsy or local procedure, within 3 weeks prior to initial dosing with Debio 1347 and/or if the subject has not fully recovered from the surgery.
 
8. Grade <math>></math> 1 NCI-CTCAE v5.0 AEs or toxicities from previous treatments except: 
 
a. Albumin (<math>\geq</math> 2.5 g/dL is allowed).
 
b. AST and ALT in subjects with liver metastases (<math>\leq</math> 5 <math>\times</math> ULN is allowed).
 
c. ALP in subjects with bone metastases (<math>\leq</math> 5 <math>\times</math> ULN is allowed).
 
d. Any grade of alopecia is allowed.
 
e. Other Grade 1-2 clinically insignificant laboratory abnormalities are allowed.
 
 
 
9. Symptomatic or unstable brain metastases <math><</math> 1 month (Of note: Subjects with asymptomatic stable and treated brain metastases are eligible).
 
10. Total corrected and/or ionized serum calcium <math>\geq</math> 1.5 <math>\times</math> UNL (corrected calcium = <math>[0.8 \times (\text{normal albumin} - \text{subject albumin})] + \text{serum calcium level}</math>).
 
11. Gastro-intestinal disorders that could affect drug absorption (including, but not limited to, gastric resection, significant bowel obstruction, active ulcerative colitis, active Crohn's disease).
 
12. Concomitant treatment with a prohibited medication.
 
13. Subjects with a known history of uncontrolled or unstable angina or myocardial infarction within the last 6 months, unstable cardiac arrhythmias despite treatment (subjects with a history of atrial fibrillation stabilized under treatment are allowed), unexplained recurrent syncope, family history of sudden death from cardiac-related causes, congestive heart failure greater than NYHA class II, uncontrolled diabetes, uncontrolled psychiatric disorders, severe ongoing infections or any other medical condition that might be aggravated by the treatment on evaluation.
 
14. Prolongation of QTcF interval to greater than 480 msec.
 
15. History of congenital long QT syndrome
 
16. History of another malignancy other than the primary tumor within the last 2 years, with the exception of completely resected basal or squamous cell skin cancer or any successfully treated in-situ carcinoma, or clinically insignificant prostate cancer without any treatment intent (either treated or on active surveillance/watchful waiting). Other cancers within the last 2 years that are considered clinically insignificant by the treating physician should be discussed with the study Sponsor to assess eligibility.
 
17. Known infection requiring the systemic use of, for example, an antibiotic or antiviral agent.
 
18. Uncontrolled intercurrent illness or psychiatric illness/social situations that would limit compliance with study requirements.
 
19. If female, pregnant or breast feeding.
 
20. Unable to swallow and retain oral medications.
 
21. Known contraindication to enhanced MRI and/or CT scan.
 

INVESTIGATIONAL MEDICINAL PRODUCT	Debio 1347 formulated as 20 mg tablets for oral administration.

TREATMENT DURATION	Subjects will be treated with Debio 1347 daily in 28-day cycles until the occurrence of disease progression (clinical or radiologic) or unacceptable toxicity (other treatment discontinuation criteria are described in Section 8.4.1).
PARTICIPANT DURATION	See above.
STUDY VISITS	
Subjects will attend a pre-screening visit (only those who undergo central assessment of FGFR status), a screening visit, a variable number of on-treatment visits depending on the number of treatment cycles, an EOT visit and a variable number of follow-up visits/contacts.
 
For all subjects who will remain on treatment with Debio 1347 after the implementation of Protocol Amendment N° 2, the assessments and procedures defined in the study protocol will no longer be in force and will be replaced by standard institutional care practice. Subjects must be followed regularly (at least every 2 months) to assess the potential occurrence of safety events, as described in the Table 8.1b.

STUDY PERIOD/DURATION	
18 months = estimated period and time in months from PPFV (first patient first visit) to LPLV (last patient last visit).
 
As of the implementation date of Protocol Amendment N° 2, subjects showing clinical benefit may continue treatment with Debio 1347 until a condition to stop treatment is met. The LPLV (last patient last visit) will occur 30 days after the end of treatment (EOT) for the last subject in the study.

STATISTICAL METHODS	
Sample size
 
A basket two stage adaptive design will be used to assess the efficacy of Debio 1347 in terms of ORR. With 27 evaluable subjects in Stage 1 and 86 evaluable subjects in Stage 2, the study will have approximately 90% power to reject the null hypothesis that <math>ORR \leq 15\%</math> when the true ORR is 30% in at least one of the baskets, using a one-sided exact binomial test at an overall significance level of 5%. The sample size for Stage 2 is for a pooled sample across baskets in case homogeneity is shown at end of Stage 1, or for one active basket taken into Stage 2 in case of heterogeneity. Sample size and design operating characteristics were determined using simulations.
 
Assuming homogeneity across baskets and a 10% drop out the study would enroll approximately 125 subjects.
 
Based on an initial statistical review of pooled data, the antitumor activity for Debio 1347 is lower than initially assumed at the time the protocol was developed. Debiopharm decided to permanently halt the enrollment in the study after consultation with the DMC on June 10th, 2020.
 
Randomisation
 
Not applicable.
 
Interim analysis
 
An interim analysis will be conducted at end of Stage 1 to assess ORR homogeneity across baskets as well as futility. A minimum of 4 subjects per basket and a maximum of 13 subjects per basket will be required for the end of Stage 1 analysis. ORR homogeneity will be assessed using a pre-defined cut-off for the critical value of the exact test for contingency tables. If homogeneity is declared, the next analysis steps will be conducted using combined data from all baskets; if heterogeneity is declared, data will be analyzed separately for each individual basket.
 
The interim analysis at end of Stage 1 will be conducted by the DMC.
 
Details on the roles and responsibilities of the DMC will be provided in the DMC charter.
 
Based on initial review and monitoring of efficacy data, the interim analysis is cancelled.
 
Efficacy analysis
 
The ITT population will be the primary analysis population for efficacy analysis. Efficacy analyses will be repeated on the mITT population and the PP population as supportive analyses. The efficacy analysis will be conducted using centrally measured response as primary analysis and repeated on locally measured response as sensitivity analysis.
 
The statistical testing for primary analysis will be conducted on ORR as centrally measured using a one-sided exact binomial test. The hypothesis tested will be:
 
 
Scenario 1: If the ORR homogeneity assumption is met at the interim analysis, then the hypothesis will be H0: ORR ≤ 15% against H1: ORR > 15% at alpha level of 5%
 
Scenario 2: If the ORR homogeneity assumption is not met at the interim analysis, then a decision will be made at the time of interim analysis to further continue the study with only 1 cohort or 2 cohorts. Then the hypothesis tested at final stage will be. H0: ORR ≤ 15% against H1: ORR > 15% in each chosen cohort
 


- Scenario 2a: In the case 1 cohort has been selected the statistical comparison will be conducted at an alpha level of 5%.
- Scenario 2b: In the case 2 cohorts have been selected the statistical comparison will be conducted at a Bonferroni adjusted alpha level of 2.5% for each cohort.

ORR, DCR and BOR will be summarized using frequencies and percentages. Confidence intervals will be presented overall and by cohort. DoR, PFS and OS will be analysed using the Kaplan Meier method.

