## 6.2. Exclusion Criteria

Any of the following would render a subject ineligible for inclusion:

1. History of hypersensitivity to any of the excipients in the Debio 1347 formulation (lactose hydrate, microcrystalline cellulose, croscarmellose sodium, hydroxypropyl cellulose, sodium lauryl sulfate and magnesium stearate).
2. Prior treatment with a FGFR1-3 selective inhibitor.
3. History and/or current evidence of ectopic mineralization/calcification, including but not limited to soft tissue, kidneys, intestine, myocardia, or lung, excepting calcified lymph nodes, lung nodules and asymptomatic vascular or cartilage/tendon calcifications.
4. Current evidence of clinically significant corneal or retinal disorder confirmed by ophthalmologic examination.
5. Chemotherapy, radiotherapy or small molecule anti-cancer agents within 2 weeks prior to initial dosing with Debio 1347 (3 weeks for immune checkpoint inhibitors).
6. Administration of any investigational agent within 2 weeks prior to initial dosing with Debio 1347 (3 weeks for immune checkpoint inhibitors).
7. Surgery requiring general anesthesia, except diagnostic biopsy or local procedure, within 3 weeks prior to initial dosing with Debio 1347 and/or if the subject has not fully recovered from the surgery.
8. Grade > 1 (National Cancer Institute Common Terminology Criteria for Adverse Events [NCI-CTCAE] v5.0) AEs or toxicities from previous treatments except:
  - a. Albumin ( $\geq 2.5$  g/dL is allowed).
  - b. AST and ALT in subjects with liver metastases ( $\leq 5 \times$  ULN is allowed).
  - c. Alkaline phosphatase (ALP) in subjects with bone metastases ( $\leq 5 \times$  ULN is allowed).
  - d. Any grade of alopecia is allowed.
  - e. Other Grade 1-2 clinically insignificant laboratory abnormalities are allowed.
9. Symptomatic or unstable brain metastases < 1 month (**Of note:** Subjects with asymptomatic stable and treated brain metastases are eligible).
10. Total corrected and/or ionized serum calcium  $\geq 1.5 \times$  UNL (corrected calcium =  $[0.8 \times (\text{normal albumin} - \text{subject albumin})] + \text{serum calcium level}$ ).
11. Gastro-intestinal disorders that could affect drug absorption (including, but not limited to, gastric resection, significant bowel obstruction, active ulcerative colitis, active Crohn's disease).
12. Concomitant treatment with a prohibited medication.

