## 7.7. Concomitant Therapy

### 7.7.1. Permitted medications

1. Supportive therapies against pain, nausea, vomiting, constipation and diarrhea are allowed as per the Investigator's decision, as well as granulocyte colony-stimulating factors (G-CSF). Treatment of pain should be administered according to severity and recommended drugs. Study specific guidelines will be provided separately.
2. Gonadotrophin-releasing hormone receptor (GnHR) agonists and antagonists for prostate cancer are permitted (if prostate cancer is the reason for eligibility).
3. Bisphosphonates and denosumab: Concomitant use is allowed.
4. Radiotherapy: Concomitant radiotherapy may only be given for the control of bone pain or as indicated to  $\leq 30\%$  of the bone marrow. Irradiated lesions will not be evaluable for response. Radiotherapy should start no sooner than 24 hours after the previous dose of Debio 1347 and study treatment may be resumed with the resolution of any radiation toxicity to  $\leq$  Grade 1.

The following medications and/or treatments are permitted with caution and should be monitored during the study:

1. Contact lenses: In non-clinical studies, Debio 1347 has been found to affect the cornea. Since corneal disorders may occur when contact lenses are worn and use of Debio 1347 may exacerbate these symptoms, caution should be exercised when administering Debio 1347 in a subject wearing contact lenses. The subject should be monitored.
2. Drugs with a known risk of QTc prolongation: Considering the QTc prolongation potential (not yet fully characterized) and the risk of hypokalemia associated with Debio 1347, caution should be exercised when using Debio 1347 with drugs having a known risk of QTc prolongation (see Arizona CERT database at website: <http://www.crediblemeds.org>). Monitoring of electrolyte levels is strongly recommended.
3. Drugs that are known substrates of either CYP3A, CYP1A2, P-gp, BCRP, MATE1 or OCT2:

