### 8.3. Study Procedures and Plan

Assessments are described in detail in Section 8.2. A study plan including timing of tests and evaluations is presented below in Table 8-1.

All eligible subjects will attend the study visits indicated in the study plan. Study procedures must be performed according to the planned time schedule with strict adherence to visit intervals.

Prior to conducting any of the screening tests, the Investigator or his/her designee will explain the study fully to the prospective subject and provide him/her with a copy of the Patient Information Leaflet/Informed Consent Form for the entire study. If the subject is willing to participate in the study, s/he and the Investigator or his/her designee will each sign two copies of the Informed Consent Form of which the subject keeps one.

Subjects who are confirmed at the pre-screening assessment as harboring FGFR fusions/rearrangements (see Section 8.2.1.1) will attend the full screening visit within 28 days prior to the first treatment cycle. Subject suitability will be confirmed by the inclusion/exclusion criteria in Section 6. A subject may be re-screened on the conditions described below.

**Of note:** Subjects who require a central assessment of FGFR status (pre-screening test, see Section 8.2.1.1) will be asked to sign a pre-screening Informed Consent Form to this intent.

As per Protocol Amendment N° 2, the updated study plan is presented in Table 8-1b.

All subjects will be followed by the Investigator as per standard institutional care practice. Subjects will receive Debio 1347 for as long as they are benefitting from the study drug and there is no safety concern as per Investigator's judgment. Pregnancy, AEs, AESI, SAEs, will be documented and collected in the study eCRF, and reported using dedicated forms described in section 9.2 of this protocol.

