### Per Protocol (PP) population

The per protocol (PP) population consists of all subjects in the ITT population who have undergone radiographic assessment at baseline (i.e., tumor assessment screening visit), received at least one dose of study drug, had both baseline and post-baseline disease and had no critical protocol deviation that may have an impact on efficacy endpoints.

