## 11.5. Statistical Analysis

### 11.5.1. General analysis methods

The statistical analysis will be described in detail in a SAP. Any deviations from the SAP, reasons for such deviations and all alternative or additional statistical analyses that may be performed, will be described in the final report.

Ordinal and continuous data will be presented in the form of descriptive statistics, as number of subjects, mean, standard deviation, minimum, Q1, median, Q3, maximum. In addition, for PK endpoints, the geometric mean, 90% confidence interval (CIs) on geometric mean, the standard deviation of the geometric mean, and geometric coefficient of variation (CV) % will be presented.

Categorical data will be presented using contingency tables with absolute and relative frequencies.

Baseline is defined as the last measurement prior to the first study drug administration.

All data analyses will be performed using SAS® statistical software and WinNonlin® Professional.

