10.1.6 Prior anti-cancer treatments

Prior anti-cancer treatments will be summarized for the ITT, mITT and PP.

Number (%) of patients with prior anti-cancer treatments will be summarized for:

- Any prior treatment with radiotherapy.
- Any prior systemic therapy.
- Any prior surgery.
- Number of previous lines of anti-cancer systemic therapy as continuous and categorical (1, 2, 3, >3).

Prior anti-cancer treatments will be summarized by ATC level 2, 4 and WHO preferred name. Best response to last prior cancer systemic therapy will also be reported.

Additionally, prior anti-cancer treatments will be listed and will include:

- Prior radiotherapy: location, dose, start and end date, number of fraction days.
- Prior anti-cancer therapy: therapy agent, therapy class, intent of therapy, line number, start and end date, reason for therapy, best overall response reached.
- Prior surgery.

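### The washout is counted back from first dose, not from the baseline scan, so shrinkage from prior treatment could enter the single-arm ORR; a flag from recorded dates would show whether it did

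*Protocol*

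**What the plan says.** **Washout.** Exclusion 5 (Protocol synopsis and Section 6.2) excludes "Chemotherapy, radiotherapy or small molecule anti-cancer agents within 2 weeks prior to initial dosing with Debio 1347", with 3 weeks for immune checkpoint inhibitors. The interval runs back from first dose.

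**Baseline scan.** Under Protocol Section 8.3, subjects "will attend the full screening visit within 28 days prior to the first treatment cycle". Section 8.2.2.1.1 and Table 8-1 place the CT or MRI in that screening period, Day -28 to Day -1. Section 11.5.1 adds: "Baseline is defined as the last measurement prior to the first study drug administration". SAP Section 9.1 says the same in substance. The per-protocol definition identifies the baseline radiographic assessment with the screening visit. None of these places the scan after the last prior treatment.

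**Progression before entry.** Inclusion 3 requires radiographic progression on prior systemic therapy. For local treatment, "prior localized therapy (i.e., radiation, ablation, embolization) is allowed provided radiographic progression out-of-field or in the treatment field is shown". Inclusion 6a allows biliary subjects further chemotherapy once gemcitabine intolerance is documented, and does not ask for progression on that later chemotherapy.

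**Irradiated lesions.** Protocol Section 7.7.1 states: "Irradiated lesions will not be evaluable for response". The sentence belongs to the item on concomitant radiotherapy.

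**Response derivation.** SAP Section 10.2.1 takes best overall response from first dose onward. It stops at progression, non-permitted concomitant treatment, new systemic therapy or withdrawal. It does not look at treatment given between the baseline scan and first dose.

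**The concern.** Two windows are anchored to first dose, and nothing links one to the other. A subject scanned early in screening could receive chemotherapy or radiotherapy after that scan, stop in time to satisfy exclusion 5, and start Debio 1347. Tumour size on study would then be compared with a scan that predates the last prior treatment. Any shrinkage from that treatment would appear as response to the study drug.

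A control arm would carry the same effect and largely cancel it. Here there is one arm, and the design tests ORR against a fixed 15%, so nothing cancels it. Confirmation at least 4 weeks later shows that a response persisted, not what caused it. With very few responders, one misattributed response would visibly change the reported rate and the waterfall plot.

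**Working it through.** **1. Length of the gap.** Inputs: screening from Day -28; washout of 14 days, or 21 days for checkpoint inhibitors.

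- Chemotherapy, radiotherapy, small molecules: 28 - 14 = 14 days in which treatment can follow the scan.
- Checkpoint inhibitors: 28 - 21 = 7 days.
- The first on-treatment scan is due at the end of Cycle 2 (day 56), so up to 28 + 56 = 84 days after baseline.

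**2. What the other rules leave open.**

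- *Systemic therapy.* Inclusion 3 does not say that progression must follow the most recent line or be shown on the baseline scan. The open route is a later line, stopped without progression and given after the scan. Inclusion 6a shows that later lines are foreseen. The route is narrow.
- *Local therapy.* Progression outside the treated field suffices, so an irradiated target lesion need not itself have progressed. Whether progression must come after the local therapy is the natural reading, but it is not stated.
- *Per-protocol set (SAP 7.4).* Baseline radiology counts as met if inclusion 7 is answered yes. A subject who violates no entry criterion stays in, whatever the order of scan and prior treatment.

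**3. One response, in observed terms.** SAP Table 6 gives unconfirmed responses at the second IDMC meeting. Removing one responder is hypothetical:

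| Reading | Observed | One fewer |
|---|---|---|
| Central, all cohorts | 3/63 = 4.8% | 2/63 = 3.2% |
| Local, Cohort 1 | 4/30 = 13.3% | 3/30 = 10.0% |

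The two-sided 95% Clopper-Pearson interval for 3/63 is 1.0% to 13.3%.

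**4. Sensitivity of the planned test.** The plan gives no figure for carry-over, so I first checked its design figures. I enumerated the two-stage design of SAP Section 6 exactly, assuming 9 subjects per cohort in Stage 1. The family-wise error with no active cohort is 5.01% (Table 1: 5%), and power with three active cohorts is 92.8% (Table 1: 92% to 93%). Agreement is looser with one active cohort (60.7% against 64%) and with two (85.4% against 87% to 88%). The equal split, against the planned 4 to 13 per cohort, may explain this.

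Let c be the share of true non-responders counted as responders through carry-over. This is an assumption; the documents give no rate. At a true ORR of 15%, the apparent ORR is 15% + 85% × c. The pooled exact test with 27 + 86 = 113 subjects rejects at 24 or more responses.

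| c | Apparent ORR | Type I error, pooled test | Family-wise error, two-stage |
|---|---|---|---|
| 0% | 15.0% | 4.7% | 5.0% |
| 1% | 15.85% | 7.9% | 8.3% |
| 2% | 16.7% | 12.3% | 13.0% |
| 5% | 19.25% | 33.1% | 34.9% |

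For example, c = 1% arises if 10% of subjects were treated after the scan and 10% of those shrank enough to count. The table shows how sensitive the planned test was. It does not estimate what happened in a study whose interim analysis was cancelled.

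**The case against.** The strongest reply is that inclusion 3 already deals with most cases. In- or out-of-field progression is naturally read as progression after the field was treated. On that reading, a subject given local therapy after the screening scan, with no later scan, is ineligible, and SAP 7.4 removes eligibility violations from the per-protocol set. If a later pre-dose scan did show progression, that scan would be the last measurement before dosing and hence the baseline. This largely stands, with two limits: the order is implied and not stated, and the primary analysis is on ITT, which keeps such subjects.

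Other parts of the reply also stand. The RECIST guideline and the imaging review charter are used but not supplied, so it is unknown whether central readers would set aside such a lesion. The counts in Table 6 are unconfirmed responses, whereas the primary endpoint needs confirmed ones. An early scan in a progressing subject can also understate tumour burden at first dose, which works against response. The net bias of an early baseline is therefore not established, although carry-over shrinkage taken alone acts upward on ORR. Its effect on duration of response is uncertain.

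A reader might infer that ablation or embolization can follow the baseline scan by nearly 4 weeks, because neither has its own interval and exclusion 7 exempts local procedures. The documents do not support this. Exclusion 7 restricts surgery under general anaesthesia and its exemption is from that restriction only; local therapy remains subject to the progression condition in inclusion 3.

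**Conclusion.** The gap is in the text and is modest. Treatment can follow the baseline scan by up to about 14 days (7 for checkpoint inhibitors), and no rule in the response derivation checks for it. The conclusion rests on reading the screening window and exclusion 5 as written, and on inclusion 3 not stating that progression must follow the most recent treatment.

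A reader might go further and infer that the reported ORR is inflated. The documents do not show that: the number of affected subjects is not given and may be zero. Nor does the point weaken the decision to stop enrolment. Counting carry-over responders as non-responders can only lower the ORR, and the upper limit of 13.3% for the pooled central unconfirmed rate is already below 15%. What is at stake is the accuracy of the reported response rate and the attribution of individual responses.

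**What to change.** In SAP Sections 10.2.1 and 10.2.1.2, before database lock:

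1. Derive a flag for each subject whose last prior anti-cancer treatment ended after the baseline scan date. SAP Section 10.1.6 already lists "Prior radiotherapy: location, dose, start and end date, number of fraction days" and start and end dates for prior anti-cancer therapy.
2. List the flagged subjects with treatment, dates, scan date and best overall response.
3. Report a supportive ITT ORR, central and local, in which flagged responders count as non-responders. Leave the primary analysis unchanged.

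If no subject is flagged, one sentence in the study report closes the matter.

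The cost is one derived variable, one listing and one supportive table. The supportive ORR may be slightly lower. The flag has a limit: the Section 10.1.6 listing names prior surgery without dates, so local procedures may not all be captured. I do not ask for a lesion-level exclusion, because the documents show no link between prior local therapy and the centrally selected target lesions.

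The sponsor should also reconcile the screening-scan window, exclusion 5, inclusion 3 and the scope of the irradiated-lesion sentence in Protocol Section 7.7.1. With enrolment permanently halted, a new scan-timing rule would reach no further subject. No washout or scan schedule is proposed here.
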